## 21.0 Statistical Considerations

**21.1** General Description: This is a single-arm, Phase II trial to characterize the clinical outcome of standard of care, cetuximab concurrent with radiation, in a special population (head and neck cancer patients who cannot tolerate concurrent chemoradiotherapy due to advanced age, poor performance status or concurrent illness), and to determine if biomarker response to a loading dose of cetuximab is predictive of that outcome.

**21.2** Number of patients: Fifty evaluable patients will be accrued to the trial, which is expected to take 36 months. A patient will be evaluable for the primary objectives if he or she undergoes Research Biopsy #1 and #2 and either completes the full course of cetuximab+RT or has cetuximab+RT stopped for toxicity. Unevaluable patients will be replaced.

**21.3** Analysis plan

**21.3.1 Primary Objective 1:** Determine changes in tumor EGFR, pEGFR, downstream signaling and novel phosphoproteins following a loading dose of cetuximab in patients who are poor candidates for chemoradiation (age  $\geq 70$  years or with significant co-morbidities) and are therefore treated with cetuximab+radiation. These markers will be assessed in tumor biopsies harvested before and after the loading dose of cetuximab. The initial analysis will use descriptive and graphical statistics to determine if any of the markers require transformation prior to analysis. Markers may be assessed on a continuous, ordinal or

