dichotomous scale; markers measured on a continuous scale will be analyzed via general linear models (possibly after transformation), while ordinal and dichotomous markers will be analyzed via cumulative logit and logistic regression analyses, respectively. The primary questions to be answered in this objective are: is the marker modulated by the loading dose of cetuximab; are there baseline clinical or demographic variables that are related to significant variation in biomarker response to the loading dose of cetuximab? For continuous variables, the null hypothesis that the mean value of the change (absolute or percent of baseline) equals zero will be tested by means of a single sample t-test. The second question will be answered by means of analysis of variance on baseline clinical and demographic variables. For dichotomous markers, patients will be stratified into elevated versus not elevated at baseline, and Wald tests on logistic regression parameter estimates will be used to test the null hypothesis that the proportion of patients changing state from baseline is different from 0.5, and to determine if any subset of patients defined by clinical or demographic factors have proportions significantly different from 0.5. Ordinal markers will be handled in a similar fashion.

[figure not shown]
21.3.2 **Primary Objective 2** Characterize clinical outcomes, including local recurrence, progression-free survival and overall survival in these patients, and correlate these clinical outcomes with the changes in tumor EGFR, pEGFR, downstream signaling, and novel phosphoproteins. Logistic regression and proportional hazards (Cox) regression will be used to relate clinical out (local recurrence, progression-free survival or overall survival) to changes in markers across the loading dose. All of the markers will be analyzed, but markers that are modulated by the loading dose (identified in Primary Objective 1) will be of particular interest.

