**21.4 Justification of Design:** While radiation with concurrent cetuximab has become the standard of therapy in patients with locally advanced squamous cell head and neck carcinoma, the clinical outcome of the therapy have not been systematically studied. In addition, therapy with cetuximab is expensive, and, while less toxic than platinum-based therapies, is not without toxicity, and a screen for patients from whom cetuximab would be of benefit would be desirable. Therefore, all patients on this protocol are treated the same, and the primary objectives are focused on comparing patients who do respond to patients who do not. Because this is the standard of care, and these patients have no other treatment options, there is no provision for halting the trial due to low efficacy or excess toxicity (although therapy can, of course, be stopped in individual patients if clinically warranted). The sample size is justified in terms of Primary Objective 2, specifically relating change in a continuous marker to progression-free survival. Monte Carlo simulation was used to simulate the analysis of a single biomarker related to progression-free survival. It was assumed that 50 patients were accrued over 36 months, that the median survival was 22 months, the proportional hazards regression was performed six months after the last patients was treated, and that the biomarker was normally distributed. The power of the null hypothesis of no marker effect (tested at  $\alpha=0.05$ ) was assessed as the effect size of the marker (here, represented as the difference between the mean of the marker for patients with PFS less than the median versus the mean of the marker for patients with PFS greater than the median, divided by the standard deviation) was increased from 0 to 1.5 standard units. The result is shown in Figure 20.1, where it is seen that the power to reject the null hypothesis of no effect is at least 80% if the effect size is 1.1 standard units or greater, which would be considered a moderately large effect.

*Figure 20.1* Power of proportional hazards regression for a marker that discriminates between patients with greater than versus less than median progression-free survival.

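### For dichotomous and ordinal markers the plan tests each clinical subset against 0.5, which does not answer its own question of whether marker response varies between subsets.

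*Combined protocol and SAP*

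**What the plan says.** Section 21.3.1 (Primary Objective 1) sets two primary questions. The first is whether the loading dose modulates the marker. The second is "are there baseline clinical or demographic variables that are related to significant variation in biomarker response to the loading dose of cetuximab".

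The answer to the second question depends on the marker's scale:

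- Continuous: "The second question will be answered by means of analysis of variance on baseline clinical and demographic variables".
- Dichotomous: "patients will be stratified into elevated versus not elevated at baseline", and then "Wald tests on logistic regression parameter estimates will be used to test the null hypothesis" on the proportion changing state, with reference value 0.5. For subsets, the same tests serve "to determine if any subset of patients defined by clinical or demographic factors have proportions significantly different from 0.5".
- Ordinal: "Ordinal markers will be handled in a similar fashion".

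No contrast between subsets is written out for dichotomous or ordinal markers. Section 21.2 fixes the size: "Fifty evaluable patients will be accrued to the trial, which is expected to take 36 months". The plan gives no subset sizes, expected change rates or significance level for Objective 1.

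**The concern.** The second question compares subsets: does the response differ by age, performance status, tumour site and so on? Analysis of variance addresses that. A test of each subset against a constant addresses something else, namely whether this subset on its own departs from 0.5. Two subsets with the same response can fall on either side of the significance line by chance, or simply because one is larger. Two subsets with different responses can both fall on the same side. Replacing 0.5 by another constant would not help.

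At stake is a statement that one clinical group's tumours respond to the loading dose and another's do not. That is the kind of finding a later trial might use to select patients. Section 21.3.1 lists this among its primary questions. Sections 21.3.3 and 21.3.5, by contrast, label their toxicity-predictor and HPV analyses exploratory.

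**Working it through.** **The plan's own figures.** None is given for this analysis. The only power statement (section 21.4) concerns a continuous marker and progression-free survival under Objective 2. It reproduces: about 25 expected events and 84-85% power at 1.1 standard units, against a stated minimum of 80%. It does not bear on this point.

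**Inputs.** From the plan: 50 evaluable patients, a logistic Wald test, reference value 0.5, and a prior split by baseline state. Assumed, because the plan is silent: two-sided alpha 0.05 (section 21.4 states 0.05 only for Objective 2); subsets of 25 v 25 or 35 v 15 out of 50, or 13 v 12 inside a baseline stratum of 25; true change rates of 50% to 80%. Results are symmetric below 50%.

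**Test in one subset.** With x of n patients changing state and q = x/n,

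z = logit(q) × √(n q (1 − q)), significant if |z| > 1.96.

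**Size alone can decide the verdict.**
- 28/40 (70%): z = 0.847 × 2.898 = 2.46, p = 0.014.
- 7/10 (70%): z = 0.847 × 1.449 = 1.23, p = 0.22.

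The observed proportions are identical (odds ratio 1), yet the verdicts differ.

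**Equal true rates, opposite verdicts.** Let A and B be the exact binomial probabilities that each subset is significant. The probability that exactly one is significant is A(1 − B) + B(1 − A).

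- 25 v 25 at 70%: A = B = 0.512, so 2 × 0.512 × 0.488 = 0.50.
- 35 v 15 at 70%: A = 0.652, B = 0.292, so 0.652 × 0.708 + 0.292 × 0.348 = 0.56.
- 13 v 12 at 70%: A = 0.193, B = 0.239, so 0.193 × 0.761 + 0.239 × 0.807 = 0.34.

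| Subsets | 50% | 60% | 70% | 80% |
|---|---|---|---|---|
| 25 v 25 | 8% | 26% | 50% | 19-20% |
| 35 v 15 | 7% | 25% | 56% | 36-40% |
| 13 v 12 (one baseline stratum) | 6% | 13% | 34-35% | 50% |

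Ranges reflect whether a subset in which every patient changed, where the Wald statistic breaks down, counts as significant. A direct Fisher exact comparison gives a false difference in 2-4% of trials over these cells.

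**Different true rates, matching verdicts.** Take 70% v 95%, 25 patients each, counting all-changed subsets as significant. The 95% subset is significant in practically every trial and the 70% subset in 51%. Both are therefore significant, in the same direction, in about 51% of trials, and exactly one in the remaining 49%. Fisher's test detects the difference in about 55%. Exactly one subset is thus significant about as often here (49%) as when both rates are 70% (50%), so in this comparison the pattern of verdicts carries almost no information about whether the subsets differ.

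**The case against.** Four points deserve weight.

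**The model could hold the right test.** Section 21.3.1 prescribes logistic regression, and with a clinical factor in the model its coefficient is the between-subset log-odds difference. But the null value stated for subsets is 0.5. A zero factor coefficient means equality at any rate, so the written criterion is a different test.

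**The plan never says how discordant verdicts will be reported.** This stands. The false difference arises when the tests are read as the answer to the plan's second question. No other test is offered for that question on these scales.

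**The size depends on assumptions.** This also stands. A reader might infer that equal subsets will usually be reported as different. The documents do not support that: 70% is close to the worst case for 25 v 25, and the figure is 8% at 50%. At 90% it falls below 1% if all-changed subsets count as significant. If they do not, it is 40% at 95%.

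A reader might also infer that large opposite-sided differences would be missed. They would not be, to any material extent. At 30% v 70% (25 each) both subsets are significant in 26% of trials, but in opposite directions, which is plain to see. Exactly one is significant in a further 50%. Some signal therefore appears in 76% of trials, against 78% for Fisher's test.

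**The reach is limited.** Appendix B averages tissue-microarray scores and uses them on a continuous scale, and immunoblot bands are quantified. Such markers go to the analysis of variance. The plan does not say which markers will be dichotomous or ordinal.

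**Conclusion.** The point holds for markers analysed on a dichotomous scale and, by reference, an ordinal one. The rule as written does not answer the plan's primary question about variation between subsets. That conclusion needs no numerical assumption.

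The size does. At an assumed two-sided 0.05, equal subsets get opposite verdicts in roughly 6-8% of trials at a true change rate of 50%. Between 60% and 80% the figure runs from 13% to 56%, depending on rate and split. It is low at extreme rates with equal subsets of 25, provided all-changed subsets count as significant. The enumeration covers dichotomous markers only; for ordinal markers the argument carries over but no figure was computed.

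It would go too far to conclude that Objective 1 as a whole is compromised, or that the sample-size justification is. The continuous branch already compares subsets directly, and the Objective 2 power statement is untouched. This should be corrected before analysis.

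**What to change.** In section 21.3.1, for dichotomous and ordinal markers, replace the subset criterion based on 0.5. Within the logistic and cumulative logit models already named, and within the baseline strata, test whether the coefficient of the clinical or demographic factor (the between-subset log-odds difference) is zero. Use a likelihood-ratio test, or Fisher's exact test where the dichotomous table is small: with 13 v 12 the likelihood-ratio test rejects equal subsets in about 6-8% of trials at rates of 60-80%, while Fisher's test stays at 2-4%. Report the odds ratio with its confidence interval. Give each subset's proportion with an exact interval as description only.

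State the significance level for Objective 1 and list which markers will be analysed on each scale.

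The cost is a sentence or two in the plan. No extra patients, samples or procedures are needed.

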### 1.1 Study Hypothesis and Rationale

Bonner *et al* investigated the benefit of the addition of cetuximab to radiation. It was concluded that cetuximab improves locoregional control and reduces mortality without increasing the common toxic effects associated with radiotherapy to the head and neck. In our study, we propose to select locally advanced head and neck cancer patients, who are older than age 70 or are not deemed candidates for chemotherapy. This group was not extensively investigated in the earlier randomized trial, in that

---

 Abbreviations: **CR**, complete response; **EGFR**, epidermal growth factor receptor; **MAPK**, mitogen-activated protein kinase; **PI3K**, phosphatidylinositol 3-kinase; **PR**, partial response; **RT**, radiation treatment/therapy; **STAT**, signal transducer and activator of transcription; **TMA**, tissue microarray.

90% of patients in the Bonner study had a KPS of 80 or greater, and the median age of the patients was 57. The primary end-point of this trial is to characterize local progression free survival in these patients, when treated with cetuximab+radiation.

We also propose to develop a molecular pharmacodynamic predictor of local control after treatment with combination cetuximab-radiation. We hypothesize that tumor EGFR degradation and other markers of down-stream EGFR inhibition as well as novel phosphoproteomic markers observed in tumor biopsies taken 7 days after the administration of cetuximab, will predict the effectiveness of cetuximab-radiation. The first biopsy will be obtained prior to administration of the loading dose of cetuximab. Prior to initiation of cetuximab concurrent with radiation, on Day 7, following the cetuximab loading dose, a tumor biopsy for the biomarkers will be obtained. We hypothesize that tumors that do not demonstrate the changes that correlate with response after cetuximab in the *in vivo* preclinical studies are more likely to progress following cetuximab-radiation therapy compared to those that show changes that correlate with response. If our hypothesis is validated, we will gain a tool that will help identify patients who are most likely to benefit from radiation and cetuximab, a very expensive and moderately toxic treatment.

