## 1.2 EGFR inhibitors in head and neck cancer

Initial *in vitro* studies demonstrated that prolonged exposure of cells to EGF could enhance the effects of radiation in head and neck cancer cells. It is likely that this radiosensitivity was achieved through EGF-induced EGFR degradation. Additional studies showed that monoclonal antibodies that target EGFR could increase radiation-induced apoptosis. Furthermore, there was an inverse correlation between EGFR expression levels and radiation response. This relationship between EGFR expression and poor prognosis was confirmed in human head and neck carcinoma samples. A variety of preclinical studies have demonstrated that EGFR inhibitors can increase radiation sensitivity in both *in vitro* and *in vivo* model systems. While the majority of studies have reported additive effects resulting from the combination of EGFR antagonists and radiotherapy *in vitro*, the same combination produces synergistic effects in xenograft models. This may be secondary to EGFR inhibitors and radiation impact on several downstream signaling pathways. These include pathways regulating cellular proliferation and apoptosis, which would

be evident in both in vitro and in vivo, and pathways regulating angiogenesis and tumor invasion, which might be detectable only in tumor xenograft models.

While preclinical studies have highlighted the potential therapeutic gains that could be achieved by adding EGFR inhibitors to radiation, the best validation of this combination has been from the results of clinical trials in head and neck cancer. A phase III clinical trial demonstrated that, in a cohort of 424 patients with locoregionally advanced squamous cell carcinoma of the head and neck, the addition of cetuximab nearly doubled the median survival of patients (compared to radiotherapy alone), from 28 to 54 months. This study represented the first major success achieved by the addition of an EGFR antagonist to radiotherapy. This improvement was achieved without enhanced toxicity. Notably, the rates of pharyngitis and weight loss were identical in the two arms.

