### 1.3 Predicting response to combination cetuximab-radiation

While we hope that we can simply substitute cetuximab for cisplatin-based chemotherapy and achieve the same rate of local control as with chemoradiotherapy without the increased toxicity of chemotherapy, we must also entertain the possibility that only a fraction of these patients will be able to achieve tumor control using this strategy. Therefore, it would be very valuable to be able to predict in advance those patients who will be able to achieve local control with cetuximab and radiation therapy. However, previous efforts to predict the response to EGFR inhibition using the pre-therapy EGFR expression levels have failed. For instance, responses to cetuximab in patients with metastatic colorectal cancer occur in the absence of EGFR staining by immunohistochemistry. Furthermore, the strength of EGFR staining using immunohistochemistry does not predict response to EGFR inhibitors combined with chemotherapy. Previous efforts to predict response in patients with head and neck cancer based on pretreatment EGFR levels have also failed. (Lung cancer may be an exception in this case as mutation of the EGFR may correlate with response, but these mutations are rare in head and neck cancer.) One other recent discovery on the biomarkers of response suggests that patients whose tumors do not have K-ras mutations have a significantly higher disease control rate than patients with K-ras mutations when treated with cetuximab in colorectal cancers. However, K-ras mutation in head and neck cancers is rare, therefore this finding will not be useful for these patients.

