21.3.3 **Primary Objective 3** *Describe the toxicity, in particular mucositis/dysphagia, of this regimen.* Adverse events will be tabulated by grade (NCI CTCAE v4), category (mucositis and dysphagia are expected to be the most common) and relatedness to treatment (not, unlikely, possibly, probably or definitely). The proportion of patients experiencing Grade 3 or worse adverse events at least possibly related to treatment will be calculated, accompanied by a 95% exact binomial confidence interval. Possible baseline demographic and clinical predictors of such toxicity may be evaluated by means of logistic regression, but, due to the low expected number of such toxicities, any such modeling will be strictly exploratory.

21.3.4 **Secondary Objective 1** *Conduct normal mucosa EGFR assessment for comparison with tumor sample.* The change in tumor EGFR level across treatment, relative to EGFR in normal mucosa, will be evaluated by means of repeated measures ANOVA.

21.3.5 **Secondary Objective 2** *Correlate HPV presence and titer with p53 status and clinical outcome.* HPV status ( $\pm$ ) will be added to the models of Primary Objective 2 to determine if +HPV patients respond to therapy differently than -HPV patients, but, due to the limited expected number of +HPV patients, such analyses will be considered exploratory.

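### Section 21.3.2 relates outcome to marker change alone and fixes no scale for it, so where baseline level is prognostic the change effect is mixed with pre-treatment level

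*Combined protocol and SAP*

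**What the plan says.** Section 21.3.2 uses logistic and Cox regression to relate local recurrence, progression-free survival (PFS) and overall survival "to changes in markers across the loading dose". It names no other term and no scale of change.

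The scale appears only in 21.3.1, for the modulation test of continuous markers, where the null is that "the mean value of the change (absolute or percent of baseline) equals zero". Transformation before analysis is also allowed there. Baseline marker level has one further use in 21.3.1: for dichotomous markers, "patients will be stratified into elevated versus not elevated at baseline". Neither provision is carried into the outcome models. The only covariate the plan adds to those is HPV status, which "will be added to the models of Primary Objective 2" as an exploratory step (21.3.5). The power simulation in 21.4 uses a single marker and no covariate.

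On interpretation, section 1.1 states the aim: "We also propose to develop a molecular pharmacodynamic predictor of local control". Section 1.2 says of EGFR: "This relationship between EGFR expression and poor prognosis was confirmed in human head and neck carcinoma samples". Section 1.3 adds: "Previous efforts to predict response in patients with head and neck cancer based on pretreatment EGFR levels have also failed".

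**The concern.** Change is usually correlated with its own starting value, because a tumor with more of a marker has more to lose. If the starting value also carries prognosis, a model with change alone credits some of that prognosis to change.

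This bears on the trial's own argument. Section 1.3 proposes that comparing pre- and post-dose specimens tells more than the pre-treatment specimen does. A change-only model cannot check that. The statement in 1.3 that pre-treatment EGFR failed to predict response does not remove the problem: a marker can fail to predict response to a drug and still be prognostic, as 1.2 says EGFR is.

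The mixing can produce an association where change has no effect of its own, or hide one where it does.

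**Working it through.** **Inputs from 21.4.** 50 patients, accrual over 36 months, median 22 months, analysis 6 months after the last patient, normally distributed marker, alpha 0.05 (taken as two-sided). Assumed: exponential PFS and uniform accrual.

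**Events.** The hazard is λ = ln 2 / 22 = 0.0315 per month and follow-up runs from 6 to 42 months. The event probability is 1 - [exp(-6λ) - exp(-42λ)] / (36λ) = 1 - (0.828 - 0.266) / 1.134 = 0.505. So 50 × 0.505 ≈ 25 events.

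**The plan's power figure.** The marker means differ by d between patients with PFS below and above 22 months, with SD 1 within each group. A one-covariate Cox model gives power of 77% at d = 1.0 and 84% at d = 1.1 (4,000 simulated trials each). The stated figure, at least 80% from 1.1 SD, is reproduced.

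**Correlation of change with baseline.** With equal pre and post variances and pre/post correlation ρ, it is r = -√((1-ρ)/2): -0.71 at ρ = 0, -0.50 at ρ = 0.5, -0.32 at ρ = 0.8.

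**Size of the mixing.** To a first approximation, the change-only log hazard ratio is r × ln(baseline HR) when change has no effect of its own. At r = -0.5 and baseline HR 2.0 this is -0.5 × 0.693 = -0.347, a hazard ratio of 0.71 per SD (simulated: 0.72). At baseline HR 1.5 it is -0.5 × 0.405 = -0.203, or 0.82 (simulated: 0.82).

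**Rejection rate of the change term, nominal 5%, no effect of change itself.** Ranges are over repeated simulations:

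| Baseline HR per SD | r = -0.3 | r = -0.5 | r = -0.7 | Baseline in model |
|---|---|---|---|---|
| 1.5 | 9% | 15–17% | 24–27% | 5–6% |
| 2.0 | 15% | 32–33% | 56–57% | 5–6% |

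With no baseline effect (HR 1.0), change-only stays at about 5%.

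**Masking.** Take a real change effect of HR 2 per SD, baseline HR 1.5 and r = -0.5. The change-only log hazard ratio falls to about 0.693 - 0.203 = 0.490 (HR 1.63). Power is 60–65% for change-only and 80–82% with baseline added.

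**Scale.** Suppose cetuximab lowers the marker by a patient-specific fraction unrelated to baseline, with baseline HR 1.75–2.0. Absolute change then rejects in 60–78% of trials; percent or log change rejects in about 5%, without any adjustment.

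**Cost at the design point.** With change truly related to PFS at d = 1.1 and baseline adding nothing, the adjusted model gives power of 79%, 77%, 72%, 65% and 54% at ρ = 0.8, 0.7, 0.5, 0.3 and 0, against about 84% unadjusted. A repeat run gave 53–80%. At ρ = 0.5 the variance inflation is 1/(1 - 0.25) = 1.33, so recovering the unadjusted power needs about 25.25 × 1.33 ≈ 34 events, or 50 × 1.33 ≈ 67 patients.

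**Noise.** Suppose both biopsies are noisy readings of one stable prognostic level, with no drug effect and reliability 0.5–0.7. Change-only rejects in about 5%. The adjusted change term rejects in 17–25% at HR 1.75–2.0 and in about 10–13% at HR 1.5. The reason is algebraic: b₁(post - pre) + b₂·pre = b₁·post + (b₂ - b₁)·pre. The adjusted change coefficient is therefore the coefficient of the post-dose value given baseline, and a second noisy reading adds information about the stable level.

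These are Cox calculations for PFS. The logistic models were not simulated.

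**The case against.** The strongest reply is that adjustment can replace one bias with another. The biopsies are about 3x3x3 mm (13.4, Appendix B), staining is scored 1 to 4 and averaged over cores (Appendix B), and the baseline may be a clinical specimen up to four weeks old (7.2.1). Noise is plausible, and under noise the change-only model is the one that holds its level. This stands, and it rules out making the adjusted coefficient the sole basis for inference.

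Second, 21.4 tests for no marker effect, which is a marginal association, and the change-only test is valid for that. This also stands. The rejection rates above are errors only against the claim that change carries information beyond baseline, which is the claim that 1.1 and 1.3 make.

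Third, percent or log change may remove the problem unaided. That is true if the drug effect is proportional, but 21.3.2 does not commit to either scale.

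Fourth, events are few: 25/2 ≈ 12 per covariate with baseline added, and 25/3 ≈ 8 if HPV status is added too. That is a reason to state the power cost, not to omit the model.

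A reader might infer that every marker is affected. The documents call only EGFR expression prognostic. A reader might also infer that the mixing would favor the trial's hypothesis. For EGFR it would tend the other way: if high EGFR is adverse and high-EGFR tumors fall further, larger falls go with worse outcome, opposite to 1.1. For the novel phosphoproteins the direction is unknown.

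**Conclusion.** The omission is real: nothing in the plan puts baseline marker value into the outcome models or fixes the scale of change there. The plan is silent on this; it does not exclude adjustment. Where baseline is prognostic and correlated with change, the change-only test rejects in about 9–57% of trials with no effect of change itself, or loses power (about 64% against 82% in the setting shown). Those sizes rest on assumed baseline hazard ratios of 1.5–2.0 per SD and correlations of -0.3 to -0.7. They show what the design permits and do not estimate this trial's error rate.

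Two stronger conclusions are not supported. One is that the adjusted model is simply the right one: with noisy biopsies it can mislead, and its power at 1.1 SD is about 53–80%. The other is that adjustment would show who benefits from cetuximab. As 21.1 says, "This is a single-arm, Phase II trial to characterize the clinical outcome"; without a control arm, even an adjusted association cannot separate benefit from cetuximab from general prognosis.

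**What to change.** In 21.3.2:

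- Prespecify the scale of change for each marker, using log or percent change where a proportional effect is expected.
- For each marker, fit and report two models side by side: change alone, and change plus the baseline value of the same marker.
- Claim a pharmacodynamic predictor independent of pre-treatment level only if the change effect is consistent in both, and define consistent in advance. Same direction in both is the minimum. Requiring significance in both would limit power to that of the weaker model.
- Do not make the adjusted coefficient the sole basis for inference. Use the replicate cores and duplicate antibody readings in Appendix B to report assay variability, noting that these do not capture all differences between biopsies.

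In 21.4, state that the 80% power applies to the unadjusted single-marker model, and give the range with baseline added.

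No new data are needed, since evaluability (21.2) already requires both biopsies. The cost is SAP wording, a second model per marker, and an open statement that 50 patients may not give 80% power for the adjusted term.
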